1 INTRODUCTION

This document is a clinical investigational plan for a human research study sponsored by Masimo Corporation. The study will be conducted in accordance with the ethical principles that have their origin in the Declaration of Helsinki. By participating in the study, the Investigator agrees to adhere to all stipulations of this protocol, the conditions of the Institutional Review Board (IRB) or Research Ethics Committee approval, federal and local regulatory requirements, 21 CFR 812, ISO-14155, International Conference on Harmonization Good Clinical Practice (ICH GCP) guidance, and Regulation (EU) 2017/745 of European Parliament and of the Council (EU MDR).

1.1 Background and Rationale

For normal cellular function, a continuous supply of oxygen is important. In case of (regional) disturbances of oxygen supply, tissue damage might ensue. Hence, maintenance of sufficient tissue oxygenation is an important target for organ protection in perioperative medicine[1]. In routine perioperative medicine, the focus of hemodynamic monitoring is on macro-circulatory variables such as heart rate and mean arterial blood pressure.[2] Nevertheless, it has been demonstrated before that macro-hemodynamic variables do not necessarily represent actual microcirculatory perfusion[3], so that adequate organ and/or tissue perfusion may be undetected and ultimately, this may lead to adverse postoperative outcome. For example, intraoperative kidney oxygenation during transplantation has been linked to postoperative graft function – and may thus be used as 'target' for perioperative hemodynamic management.[4] In addition, somatic (systemic) oxygenation may be helpful as a guide in resuscitation of critically ill patients with circulatory shock[1,5,6].

In the past decade, technologic advances allow the non-invasive, bed-side measurement of regional oximetry using near-infrared spectroscopy (NIRS). In NIRS, near-infrared light is transmitted through the skin using a non-invasive adhesive probe. The resulting reflected light as obtained by this probe is suggested to resemble regional tissue oxygenation by measuring the ratio of oxyhemoglobin to total hemoglobin in an assumed arterial / venous ratio (typically 30:70 or 25:75, depending on the manufacturer)[7]. Multiple NIRS monitors are currently available on the market. Most frequently, NIRS sensors may be placed on the overlying skin of the tissue(s) of interest, to provide tissue oxygen saturation of that particular region for monitoring oxygenation of that particular region or as an assessment of overall somatic oxygenation[7].

The Masimo O3 regional oximeter (Masimo Corp, Irvine, USA) has been developed recently. This device allows measurement of somatic tissue oxygen saturation (rSO_2) at different sites. Obviously, it is of paramount importance that NIRS readings are reliable during different states of oxygenation, especially during hypoxia. While rSO_2 trending in somatic tissues has been assessed previously[8], and the O3 device has recently received FDA clearance and CE marking for rSO_2 trending in somatic tissues, its absolute accuracy in monitoring rSO_2 in somatic tissues has not been determined yet.

To assess whether somatic rSO_2 values match with microcirculatory oxygenation of the tissue of interest, both the afferent (arterial input) and efferent (venous output) oxygenation needs to be assessed. Hence, in absence of any major circulatory pathology that would influence arterial oxygenation, this is generally derived from a radial artery catheter (SaO_2) and from a venous catheter (SvO_2) as close to the tissue of interest as possible[9].

One study in healthy volunteers examined the absolute and trend accuracy of the O3 oximeter previously. In this study cerebral rSO_2 was measured continuously on the forehead and reference blood samples were taken from the radial artery and internal jugular bulb vein, at baseline and after inducing hypoxic states. This study enrolled 27 subjects and found acceptable absolute and trend accuracy of the rSO_2 measurements when compared with the reference gold standard. [REDACTED]

A method agreement study was also done in the clinical setting, in which peripheral somatic rSO₂ readings of the O3 device were compared with those measured with another device (EQUANOXTM 7600, Nonin Medical Inc, Plymouth, USA) in cardiac surgical patients. This study suggested that both devices cannot be used interchangeably. A limitation of this study was that the O3 device was not compared to the gold standard (gradient between arterial and venous oxygen saturation).

In this study, controlled hypoxia will be induced in healthy volunteers while Masimo O3 regional oximeter-derived rSO₂ readings of somatic tissue [REDACTED] will be measured. These readings will be compared with SaO₂ and venous sheath-derived reference SvO₂ values [REDACTED]

2 STUDY DEVICES

2.1 Study Devices Used

- Masimo Radical-7® Pulse Co-Oximeter®
- Masimo Root® Patient Monitoring and Connectivity Platform
- Masimo O3® Regional Oximeter
- Masimo O3® Adult rSO₂ Adhesive Sensors
- Masimo RD SET™ Adult SpO₂ Sensors

2.2 Device Accountability

2.2.1 Receipt of Study Device

Masimo may ship or hand-carry devices and sensors to the investigative sites. Upon receipt of the study device supplies, an inventory must be performed and the Equipment Shipment Check Form (FRM-2713) and the device accountability log will be completed for each device and signed by the receiver. It is important that the designated study staff counts and verifies that the shipment contains all the items noted in the shipment inventory. Any damaged or unusable study devices in a given shipment will be documented in the study files. The investigator must notify the study sponsor of any damaged or unusable study devices that were supplied to the investigator's site.

2.2.2 Use of Study Device

Use of devices and sensors will be documented on Case Report Forms (CRF) for each subject. Any unused devices must be returned to the Sponsor at the end of the study or before product expiration date.

2.2.3 Return or Destruction of Study Device

At the completion of the study, there will be a final reconciliation of study devices. This reconciliation will be logged on the device accountability log. Any discrepancies noted will be investigated, resolved, and documented prior to return or destruction of unused study devices. Devices destroyed on site will only be upon written instruction from the Sponsor and will be documented in the study files.

2.2.4 Device Deficiency

Device deficiency is defined as inadequacy of a medical device with respect to its identity, quality, durability, reliability, safety or performance. Device deficiencies include malfunctions, use errors, and inadequate labeling. (ISO 14155:2011 3.15). All Masimo device related deficiencies should be reported to the Sponsor and must be recorded in the CRF in a timely manner. This excludes computer issues. These should be reported to the IRB/ethics committee as required per local

requirements. The sponsor shall also report to the Member State any device deficiency that might have led to a serious adverse event if appropriate action had not been taken, intervention had not occurred, or circumstances had been less fortunate. When a Masimo device deficiency is observed, every effort should be made to return the device and its packaging to the Sponsor in a timely manner.

3 STUDY OBJECTIVES

3.1 Primary Objective

The primary objective is to validate Masimo O3 regional oximeter-derived somatic rSO₂ readings in healthy volunteers under controlled hypoxia, by comparison of these readings with SaO₂ / SvO₂ blood reference values as the gold standard.

[REDACTED]

[REDACTED]

[REDACTED]

4 STUDY DESIGN

4.1 General Design

This study is a prospective, single-center healthy volunteer validation study.

[REDACTED]

If the volunteer decides to participate in this study, informed consent is explained and a copy is handed over or sent by email and a date is set for the screening visit, and for the hypoxia procedure study session, which will be at least 24 hours after obtaining informed consent. A screening blood and urine test will be performed as well as physical examination and ECG recording. All inclusion criteria and exclusion criteria needs to be confirmed before a volunteer is eligible for the study and can be assigned a study number. For women, a negative pregnancy test must be confirmed before the onset of study session.

To derive a representative population sample size, volunteer inclusion will be stratified to skin pigmentation, and at least 4 subjects should have a dark skin pigmentation. Skin pigmentation will be assessed using the Massey Scale[10].

The names and study numbers of those who sign a consent form will be recorded in an enrollment form stored in a password protected electronic file. Demographic data (ASA physical status classification, age, gender, weight, height, skin pigmentation, co-morbidity, and regular medication history) will be recorded in a case report form (CRF) kept separate from any subject identifiable data. After IRB/ethics committee approval for the study and written informed consent of each volunteer, the volunteers will undergo the study session. The study will take place in a controlled environment at

[REDACTED]

UMCG, under supervision of at least one qualified anesthesiologist.

[REDACTED]

We aim to include 25 subjects in the study, and withdrawn subjects will be replaced by another volunteer. Therefore, several extra subjects are recruited to account for withdrawn subjects and screen-failures. Subjects who did not complete the study procedures due to errors of technical nature and who did not meet any of the stopping criteria during the procedure, can be asked to repeat the study procedures.

[REDACTED]

4.2 Study Endpoints

4.2.1 Primary Endpoint

The primary endpoint for this study is to assess regional oximeter-derived somatic rSO₂ with Masimo O3 sensors and to compare this to invasively determined somatic oxygenation values (SaO₂ / SvO₂) during normoxia and

controlled hypoxia [REDACTED]
[REDACTED]
[REDACTED]
[REDACTED]

4.4 Population Base

Subjects will be healthy men and/or women between 18 and 45 years of age (inclusive) consisting of members of the community at large. At least 4 subjects should have a dark skin pigmentation, in order to have a representative sample size.

4.5 Number of Subjects

A total of 25 subjects may be enrolled at the Clinical Site. Withdrawn subjects will be replaced by another volunteer. Therefore, several extra subjects are recruited to account for withdrawn subjects and screen-failures. Subjects who did not complete the study procedures due to errors of technical nature and who did not meet any of the stopping criteria during the procedure can be asked to repeat the study procedures. If the subject is willing to discuss repeating the study session, a person who is independent from the study will discuss this with the subject to ensure they do not feel obligated to do so and there is no serious error. If, after this discussion, they still want to return for a second study session, informed consent will be obtained a second time and a second study session will be scheduled. If a subject were to repeat the study procedures, the subject would receive financial compensation for performing the study procedures a second time.

4.6 Inclusion Criteria

In order to be eligible to participate in this study, a subject must meet all of the following criteria:

- Age between 18 and 45 years, inclusive
- Willing and able to provide written informed consent
- Healthy subjects

4.7 Exclusion Criteria

A potential subject who meets any of the following criteria will be excluded from participation in this study:

- Pregnant women
- Presence of any cardiovascular or pulmonary disease
- Exposure to high altitude(s) (>2000 m) within 30 days prior to the study
- Known allergy to intravenous contrast medium or heparin
- Subject has skin abnormalities affecting the digits such as psoriasis, eczema, angioma, scar tissue, burn, fungal infection, substantial skin breakdown, nail polish or acrylic nails that would prevent monitoring of SpO₂ levels during the study
- Patients deemed not suitable for the study at the discretion of the Investigator

5 STUDY PROCEDURES

5.1 Subject Recruitment and Screening

Volunteers will be recruited by the UMCG research group. [REDACTED]

The complete study will take place at [REDACTED] UMCG that will be equipped with all required study and safety equipment. All volunteers will be selected and screened for eligibility in the study by a certified physician in the [REDACTED] of the UMCG. All volunteers will fast for solid foods for at least 6 hours before the start of the study. The volunteer is allowed to drink clear fluids until 2 hours before the start of the study. No premedication will be administered. All participants will be encouraged to restrain from alcohol on the day prior to the study.

5.2 Informed Consent

The study staff delegated for this task are responsible for conducting the consent process and for obtaining consent, prior to each subject's inclusion into the study. The Investigator shall not allow subjects to participate in the study or consent any subjects prior to receiving IRB/ethics committee approval of the consent process. Informed consent may be obtained directly or via mail.

The study staff will thoroughly explain the purpose and procedures of the study, the subject's involvement and responsibilities, the potential risks and benefits of participation, the subject's rights and privacy of the data collected, and that participation is voluntary. Subjects will be given 7 days to ask questions regarding the study. Once all questions have been answered and the informed consent signed, the subject will be enrolled in the study. If the subject refuses to participate, they will not be enrolled in the study. The subject will be assigned a non-identifying subject number for the data collected in this study, and the names and study numbers of those who sign consent forms will be recorded in an enrollment form stored in a password protected electronic file. The Investigator shall retain a copy of the signed informed consent document in each subject's record, and the subject shall be provided with a copy of the signed informed consent document.

Once a volunteer decides to participate in the study and informed consent is obtained, screening can be started. The hypoxia procedure will be at least 24 hours after obtaining informed consent. Prior to the onset of study sessions, all subjects will perform screening blood- and urine tests as well as an ECG. Women will also undergo a pregnancy test before their study session.

5.3 Treatment of Subjects

Each subject will undergo the following interventions in a standardized sequence:

- Stepped Hypoxia Plateau Sequence Protocol by changing inspiratory oxygen fraction (FiO₂):
 - Normoxia: room air (FiO₂ 0.21) (baseline)
 - Hypoxia [REDACTED]
[REDACTED]
[REDACTED]
- After measurements have been completed, the subject will be allowed to breathe room air.
[REDACTED] oxygen saturation (SaO₂ or SvO₂, respectively) will be measured by drawing blood samples [REDACTED]

5.4 Study Procedures

- O3 rSO₂ sensors will be applied before each study session.
- All subjects will have their medical history done at the time of the screening period. Female subjects will have a pregnancy test prior to being admitted to the study.
- Upon passing the screening tests, each subject will read and sign an Informed Consent to Act as a Human Research Subject form prior to being enrolled in the study.

- A (20G) radial artery catheter will be inserted in the radial artery of the non-dominant hand. It will be inserted under local anesthesia (Lidocaine), only after the Allen Test is negative. The arterial catheter will be used for SaO_2 measurements and for continuous monitoring of arterial blood pressure.

- The venous sheath and radial artery will be continuously flushed with NaCl 0.9% by a pressure infusion bag (per institutional policy).

- The Masimo O3 regional oximeter rSO₂ sensor will be placed on the skin [REDACTED]
[REDACTED]
The rSO₂ sensors may be placed on the forehead as well.

The rSO₂ sensors may be placed on the forehead as well.

- The face-mask will be applied to the subject and it will be connected to the breathing circuit. Note, the subject will still breathe room air at this moment.

- Hypoxia Plateau Sequence Protocol by changing inspiratory oxygen fraction (FiO_2):

After all catheters and sensors have been placed, the following intervention(s) will be applied during the stepped hypoxia plateau sequence:

- o Baseline blood samples will be obtained

Hypoxia breathing mixtures of O₂ / N₂ in air via a tight-fitting facemask.

- After measurements have been completed, the subject will be allowed to breathe room air.
- A study event flowchart of the stepped hypoxia plateau sequence is given below (figure 1).

- Recovery Period:

- The volunteer should remain in bed for one hour, and will be monitored using the remaining basic monitoring (see above) for another hour.
- The volunteer will be allowed to go home after the medical personnel determine that it is safe to do so. The volunteer should not drive a car by themselves, until 1 day after the study procedure. The volunteer is asked to refrain from strenuous exercise the first 48 hours after the study procedure.

- All blood samples will be immediately analyzed using satellite-lab blood gas analysis.

Early Termination Conditions: At any point in the study, if the subject feels uncomfortable, the subject will be given 100% oxygen and the study interrupted/stopped. For the safety and welfare of the subjects, the study will be prematurely terminated if any of the following conditions are met: a rise or fall in arterial blood pressure of more than 30% from baseline, a rise in heart rate to 130 BPM or greater, dysrhythmia, complaints of feeling faint, altered mental status, clinical

suspicion of an allergic reaction, or if the subject requests the study to stop for any reason. In the unlikely event that a drug-related allergic reaction is suspected, the study will be stopped directly and if required, the infusion of the drug will be halted. All routinely available drugs and monitoring equipment is directly available for treatment of an allergic reaction. The attending researcher-anesthesiologist is experienced in the management of allergic reaction.

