12 ADMINISTRATIVE ASPECTS

12.1 Protection of Human Subjects

In accordance with EU MDR and 21 CFR 50, written consent must be obtained from each subject prior to any study procedures in accordance with applicable federal, state, and study site regulations. The Investigator must keep a copy of the signed consent form in each subject's record and provide a copy to the subject as well. The Investigator shall not allow a subject to participate in a study or sign consent prior to IRB/ethics committee approval. Oral consents may be used in the study with approval by IRB/ethics committee.

Prior to the start of data collection or subject enrollment, the Investigator must provide documentation of IRB/ethics committee approval of the study protocol and a copy of the approved informed consent form (EU MDR, 21 CFR 50).

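### Section 5.4 puts the consent signature after the screening tests, contradicting sections 5.2 and 12.1, which put it first; the passages must be reconciled

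*Combined protocol and SAP*

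**What the plan says.** Three sections of the protocol fix the order of consent and screening.

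- Section 5.4 (Study Procedures): "Upon passing the screening tests, each subject will read and sign an Informed Consent". The bullet goes on to place this step before enrolment.
- Section 5.2 (Informed Consent): "Once a volunteer decides to participate in the study and informed consent is obtained, screening can be started".
- Section 12.1 (Protection of Human Subjects): "written consent must be obtained from each subject prior to any study procedures".

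The content of screening is given elsewhere. Section 4.1 has "A screening blood and urine test will be performed as well as physical examination and ECG recording", and section 5.2 has "all subjects will perform screening blood- and urine tests as well as an ECG". Section 5.4 itself does not list the tests.

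On the form of consent, section 4.6 makes it an inclusion criterion that a subject be "Willing and able to provide written informed consent", and section 4.1 also refers to each volunteer's consent as written. Section 12.1, after its written-consent rule, adds: "Oral consents may be used in the study with approval by IRB/ethics committee".

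**The concern.** The order in 5.4 is the reverse of the order in 5.2 and 12.1. Section 5.4 sits in the operative part of the protocol, where staff look to see what is done to a subject. A site that took its bullet at face value would draw blood, collect urine, record an ECG and examine a volunteer before that volunteer had signed, and in doing so would breach section 12.1.

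This matters in this population. Section 7 says that enrolled subjects gain no benefit, and section 9.1 allows recruitment of economically or educationally disadvantaged people. Consent ahead of any procedure is the protection that the protocol itself sets for them. A breach touching subjects' rights could also have to be reported as a deviation under section 8.7, and here it would arise from following the protocol.

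**Working it through.** No arithmetic bears on the order of two steps, so the check is a comparison of the texts.

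**Step 1. Write out the order that each section gives.**

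| Section | Order |
|---|---|
| 5.4 | screening tests passed → form read and signed → enrolment |
| 5.2 | consent obtained → screening starts → hypoxia session |
| 12.1 | written consent → any study procedure |
| 4.1 | consent explained and a copy given, screening date set → screening; time of signing not stated |

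**Step 2. Are the screening tests study procedures in the sense of 12.1?** Yes, on any ordinary reading. Blood and urine tests, an ECG and a physical examination are done on healthy volunteers solely to decide whether they can enter this study. They are not a review of existing records.

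**Step 3. Is there a reading that satisfies all three?**
- *Section 4.1 as tie-breaker.* It has consent explained and a copy given when the screening visit is arranged, but does not say when the form is signed. It is compatible with either order and settles nothing.
- *The 5.4 form as a second consent.* The bullet has the subject both read and sign at that point, which describes the consent step itself and not confirmation of one already taken. The visible text describes one consent process. The only second consent it mentions is in section 4.5, for a subject who repeats the session after a technical error.
- *Oral consent before screening, signature later.* Section 12.1 permits oral consent only with ethics committee approval. Section 5.4 mentions no oral step, and the written-consent rule in 12.1 still applies ahead of procedures.

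None of these reconciles 5.4 with 5.2 and 12.1.

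**Step 4. Who would be affected if 5.4 were followed literally?** Everyone screened. Those who pass would sign late. Those who fail would never reach the consent step, because signing is conditional on passing. The target is 25 subjects (sections 4.1 and 4.5), with withdrawn subjects replaced. The protocol expects screen failures but gives no number, so the total cannot be stated beyond 25 plus replacements plus screen failures.

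**Step 5. Would the protocol's own checks catch it?** Not reliably. Section 11 has the monitor confirm that consent is present. Section 10.3 says the CRF may record whether consent came before the start of the study. Section 13 requires consent before enrolment. A signature given after screening but before enrolment could pass all three and still break 12.1.

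**Step 6. Are the endpoint data affected?** No. Even in the order of 5.4, the signature comes before enrolment and is listed ahead of catheter placement and hypoxia. Section 4.1 separately requires written consent before the study session. Every rSO₂, SaO₂ and SvO₂ value for the primary comparison would follow a signature.

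**The case against.** The strongest reply is that one stray bullet stands against two clear statements, one in the section devoted to consent and the other a mandatory rule. The bullets in 5.4 are not strictly chronological either: sensor application comes first and is described again later, and the immediate analysis of blood samples appears after the recovery period. A competent site would probably follow 5.2. This stands as far as likelihood goes, and it makes exposure of every volunteer a worst case. It does not remove the contradiction, because the bullet states its own sequence in words and does not rely on its position in the list.

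A reader might also infer more than the documents support:

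- *That subjects would be tested without any consent.* Section 4.1 has consent explained and a copy supplied when the screening visit is set. What 5.4 lacks before screening is signed consent.
- *That the pregnancy test precedes consent.* Section 5.4 ties it to admission to the study, and 4.1 and 5.2 tie it to the study session. Its order relative to the signature is only an inference.
- *That the 24-hour interval before hypoxia becomes ambiguous.* Sections 4.1 and 5.2 both count it from the obtaining of consent. The conflict may move the date of signing, but it creates no second definition of the interval.
- *That data would be lost, at 1/25 = 4% of the sample per subject.* Nothing in the documents says that such data would be discarded, and all endpoint data follow a signature under either order.

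On oral consent, the reply is that the sentence is conditional on ethics committee approval and may be standard wording for an approved exception. That is fair: the sentence needs clarifying, and the documents do not show that it must be deleted.

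**Conclusion.** The point holds: section 5.4 is wrong as written. Its consent bullet contradicts sections 5.2 and 12.1, and the three cannot all be followed. The consequence is confined to screening. If 5.4 were followed literally, volunteers would have blood and urine tests, ECG and physical examination before signed consent, and screen failures would never sign. There is no effect on sample size, endpoint data or analysis. The case for acting rests on subject protection and compliance, and on how little the correction costs.

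The conclusion rests on two assumptions: that the screening tests count as study procedures under 12.1, and that no separate screening consent is described in the parts of sections 4.1, 5.1 and 5.4 that are blacked out. Even if one were, the visible 5.4 bullet would still need to refer to it.

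The oral-consent sentence is a lesser inconsistency. It sits awkwardly with the written-consent requirement in the same section and in 4.1 and 4.6, and no circumstance is given in which it would apply.

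**What to change.** Reword the 5.4 bullet so that each volunteer reads and signs the written consent form before any screening test, and so that passing the tests leads to the study session and not to the signature. This brings 5.4 into line with 5.2 and 12.1 and imposes nothing new. Stating the time of signing in 4.1 as well would close the remaining gap.

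Secondly, reconcile the oral-consent sentence in 12.1 with the written-consent requirement in 12.1, 4.1 and 4.6, either by saying when oral consent could apply and how it relates to the signed form, or by removing it if no such case is intended.

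The cost is one reworded bullet, one clarified sentence and, optionally, a phrase in 4.1, made at the next amendment. Sample size, schedule of measurements and analysis do not change.
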